### 7. EVALUATION TOOLS

### 7.1 Investigator Evaluation Standard 2D Photography

Two-dimensional (2D) facial photographic images will be captured by the Canfield Scientific, Inc. VISIA CA imaging system.

- The camera system standardizes the facial (front, left and right oblique) images captured and lighting modalities.
- All makeup should be removed, hair pulled back in consistent manner and behind the ears, all jewelry removed.
- Patients will be notified in their informed consent about the collection and use of their photographs for research purposes which may be used for scientific, educational presentations or publications.

The data will be comparing baseline photos to 1- and 3-months post treatment for results.

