#### 6.5.2 Specimens

Five patients who provide additional consent to provide biopsies will have three (3) punch biopsies taken by the Investigator or site designee in the treatment area (area of photodamage). Location of biopsies will be pre-auricular, at temporal hairline, or the forearm. Pre- and post-treatment biopsies must be taken from the same general location for each patient.

- The first biopsy will be collected at Screening/Baseline visit (pre-Treatment #1)
   The first treatment will be subsequently scheduled at the discretion of the principal investigator as they determine the biopsy site to be healed for treatment
- The second biopsy will be collected at 14 days following the first treatment.
   The second treatment will be subsequently scheduled at the discretion of the principal investigator as they determine the biopsy site to be healed for treatment.
- The third biopsy will be collected at 3-month follow up (3-months post final treatment, Treatment #4).

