### 7.3 Punch Biopsies

Up to five (5) subjects will be consented to provide skin biopsies. Each subject will provide up to three (3) punch biopsies. 2 mm punch biopsies will be taken from the location on the face in an area of photoaging at discretion of investigating physician either pre-auricular or at temple hairline. If face location is unattainable the forearm (exposed to photoaging) may be used as an alternate biopsy location and will receive the combined laser treatment in addition to receiving a facial treatment. Pre- and post-treatment biopsies must be taken from the same general location for each patient.

[figure not shown]
Biopsies will be obtained using standard sterile technique after an intradermal local anesthesia, closed with suture (at the discretion of the Sub-Investigator/Study Physician), and treated with topical antibiotic and sterile dressing in routine fashion. Subjects' skin may be marked with a surgical marker to use as reference. Complete anesthesia of the biopsy site will be confirmed prior to the punch being inserted.

The biopsies will be immediately transferred into 10% formalin solution and stored at room temperature. Collected biopsy samples will be sent to Propath for biopsy sample analysis. IHC staining for Procollagen I, elastin, CD31, lymphocyte count, Masson's trichrome, GAG (Colloidal/Fe), and H&E, with images. 15 samples total will be collected (5 sets at baseline, day 14 and final visit).

The biopsy sample manifest will be sent to Propath and will contain the subject number, product information, total number of biopsies collected, and any other relevant information needed to identify the samples post-analysis.

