### 7.7 Independent Photographic Assessments

Two experienced, blinded photographic reviewers will compare 2D photographs via Canfield Scientific, Inc VISIA data access system:

- The reviewer will select between 2 sets of unmarked photos and determine which
  is baseline and one-month post treatment. Based on their selection of baseline to
  one-month post treatment the reviewer will rate improvement.
- 2. The reviewer will select between 2 sets of unmarked photos and determine which is baseline and three-months post treatment. Based on their selection of baseline to three-months post treatment they will rate improvement.

A Quartile Improvement Scale will be used to individually score each category: (a) fine wrinkles, (b) skin texture, (c) dyschromia/pigment, (d) skin radiance, (e) pore size and (f) overall appearance.

Blinded Investigator Quartile Improvement Score			
Rating	Percentage (%)	Score	
No Improvement	0%	0	
Minor/Mild Improvement	1%-25%	1	
Moderate Improvement	26%-50%	2	
Marked Improvement	51%-75%	3	
Very Significant Improvement	76%-100%	4	

If the incorrect order is selected that grouping will not be used to calculate improvement. The percentage of correct to incorrect will be calculated for both one-month and three-month assessments.

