### 9.2.3 Biopsy Risks

Skin Biopsy - There will be temporary discomfort when the local anesthetic is injected and when its effect wears off. Some slight bleeding may occur after the biopsy. There is a rare risk of infection. The biopsy may leave a small scar. The scar may be permanent.

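### In up to five subjects, facial biopsy marks may differ between the baseline and follow-up photographs, giving the blinded reviewers an ordering cue unrelated to photoaging

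*Combined protocol and SAP*

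**What the plan says.** **Biopsies.** Section 7.3: "Up to five (5) subjects will be consented to provide skin biopsies", and "Each subject will provide up to three (3) punch biopsies". The punches are 2 mm, from a "location on the face in an area of photoaging at discretion of investigating physician either pre-auricular or at temple hairline". The alternate: "If face location is unattainable the forearm (exposed to photoaging) may be used as an alternate biopsy location". Section 6.5.2 repeats the three sites ("Location of biopsies will be pre-auricular, at temporal hairline, or the forearm") and keeps all of a subject's biopsies in the same general area. Section 9.2.3 warns: "The biopsy may leave a small scar. The scar may be permanent".

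**Photographs.** Section 7.1 specifies front, left oblique and right oblique views, without makeup and with "hair pulled back in consistent manner and behind the ears".

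**Blinded read.** Section 7.7 gives two blinded reviewers an ordering task: "The reviewer will select between 2 sets of unmarked photos". They name the baseline set and then score improvement from 0 to 4. Wrongly ordered sets are left out of the improvement score, and the correct-order percentage is reported at one and three months. The SAP table in section 10.2.2 tests the blinded scores against 0 with a Wilcoxon signed rank test. It has no test of order accuracy.

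**Role of the read.** Section 4.2.4 lists it as exploratory. Section 10.2.3 is a single sentence, naming blinded photo evaluation as the means of limiting bias. Neither section 7.7 nor section 10 mentions masking, or separate handling of biopsied subjects.

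**The concern.** Asking reviewers to order the photographs is a useful check only if they must rely on visible change in photoaging. A biopsy mark that differs between the two photographs gives them something else to go on. The ordering also decides which sets count, since only correctly ordered sets contribute improvement scores. A cue from the biopsy can therefore change both the reported correct-order percentage and the group of subjects whose blinded scores are summarised.

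The study has no control group, and section 7.2 has the treating investigators score the primary endpoint from photographs whose order they know. A reader who wants reassurance about bias has only the blinded read to turn to.

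**Working it through.** **1. Sequence of events** (sections 6.5.2 and 6.8)

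- Visit 1, at most 30 days before Treatment 1: biopsy 1.
- Visit 2: baseline photograph, then Treatment 1. Same-day screening and treatment is allowed only for subjects without biopsy.
- Visit 2a, 14 ± 7 days after Treatment 1: biopsy 2.
- Visit 6: one-month photograph. Treatment 4 is about 3 months after Treatment 1, so this is about 4 months after Treatment 1, and the biopsy 2 site is about 4 − 0.5 = 3.5 months old.
- Visit 7: three-month photograph, about 6 months after Treatment 1, with the biopsy 2 site about 6 − 0.5 = 5.5 months old. Biopsy 3 is at this visit. Its order relative to the photograph is not stated, though the visit list puts photography first.

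The baseline photograph may thus show one mark up to about a month old, and each follow-up photograph two older marks. The count of marks points to the right order; their freshness may point to the wrong one. Section 6.2 also lists photographs among the assessments made in the 30 days before the procedure. If the baseline photograph preceded biopsy 1, the contrast would be no mark against two. The schedule in section 6.8, however, places photography at Visit 2 and not at Visit 1.

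**2. Effect if the cue reveals the order**

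The plan gives no expected correct-order rate, so there is no figure to reproduce and a range is used. Let N be the subjects read, k those correctly ordered because of the mark, and p the correct-order rate in the rest. For each reviewer:

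- reported rate = ((N − k)p + k)/N
- rise over p = k(1 − p)/N

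Rise in percentage points, for the planned maximum of 30 and the powered sample of 25 (section 10.1):

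| N | k | p = 50% | p = 70% | p = 90% |
|---|---|---|---|---|
| 30 | 1 | 1.7 | 1.0 | 0.3 |
| 30 | 3 | 5.0 | 3.0 | 1.0 |
| 30 | 5 | 8.3 | 5.0 | 1.7 |
| 25 | 1 | 2.0 | 1.2 | 0.4 |
| 25 | 3 | 6.0 | 3.6 | 1.2 |
| 25 | 5 | 10.0 | 6.0 | 2.0 |

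Example: N = 30, k = 5, p = 0.5 gives (25 × 0.5 + 5)/30 = 17.5/30 = 58.3%, against 50%.

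**3. Share of the scored sets**

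The k subjects supply k/((N − k)p + k) of the sets that are scored. For N = 30 and k = 5 this is 5/17.5 = 28.6% at p = 50% and 5/27.5 = 18.2% at p = 90%.

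**4. Effect if the cue misleads**

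If k subjects are ordered wrongly because of the mark, the rate is (N − k)p/N, a fall of kp/N. For N = 30 and k = 5 it becomes 12.5/30 = 41.7% at p = 50% (down 8.3 points) or 22.5/30 = 75.0% at p = 90% (down 15.0 points). Those five subjects then drop out of the blinded improvement score.

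**The case against.** The case against has four parts.

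- **The marks may not be readable.** A 2 mm punch near the hairline may heal to something faint. Section 9.2.3 says only that a scar is possible, and a subject biopsied on the forearm gives no facial cue. This stands: five is a ceiling, and the number affected could be small or zero.
- **The cue need not point the right way.** Biopsy 1 precedes the baseline photograph, so the fresher mark may be in that photograph. Nothing in the documents says that reviewers know who was biopsied or when. This also stands. A reader might infer that the marks make correct ordering certain in five subjects; the documents do not support that. A misleading cue is still a cue unrelated to photoaging, so the point survives in two-sided form.
- **The read is exploratory.** This stands. At full enrolment at least 25 of 30 subjects carry no biopsy cue.
- **Image handling may be specified elsewhere.** Section 6.2 refers to an image capture document and section 6.5.1 to a photography manual, neither of which was available. Masking could be described there. If so, section 7.7 should refer to it.

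A reader might also treat order accuracy as a test against 50% and compute an inflated false-positive rate. Under pure guessing, the chance of 21 or more correct of 30 is 2.1%; with five subjects certain to be ordered correctly it is 11.5%. That calculation belongs to a test the plan does not contain, and it assumes that all five sites are facial, visible and correctly interpreted.

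**Conclusion.** The concern holds in a limited form. In up to five subjects, biopsy marks may differ between the photographs being ordered, and this can reveal or mislead in the exploratory read that section 10.2.3 relies on as its only bias control.

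If the cue reveals the order, the reported correct-order rate among 30 subjects rises by 1.7 points (one subject) to 8.3 points (five subjects) when reviewers otherwise guess, and by 1.7 points for five subjects when accuracy elsewhere is 90%. These figures assume that each affected subject has a facial site, a visible mark and a correct interpretation by the reviewer. The documents establish none of the three for any given number of subjects. The effect on the 0–4 blinded score cannot be sized from the documents. No false-positive rate applies, because no test of order accuracy is planned.

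A reader should not infer that the primary or secondary endpoint is compromised by this. Both are scored by treating investigators who already know the order. The point is a modest one, worth acting on because the protection is nearly free.

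**What to change.** In section 7.7 and in the blinded-investigator row of the SAP table, state that the following will be reported both for all subjects and with subjects biopsied on the face excluded:

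- the correct-order percentage, at one and three months;
- the blinded improvement scores, with their Wilcoxon signed rank test.

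This requires each biopsied subject's site (face or forearm) to be on record. It should be written in before the blinded read begins. The cost is one extra table and a slightly smaller sample in the sensitivity analysis: 30 − 5 = 25 subjects, or 25 − 5 = 20, before wrongly ordered sets are removed.

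Optionally, where the photography vendor can do it, mask the biopsy area identically in both photographs of each set before the blinded read. This prevents the cue instead of only showing its effect, but it leaves a small strip of treated skin unrated. Applied to every subject, it would also make the blinded read cover slightly less of the face than the investigator's read. The sensitivity table is therefore the main recommendation and masking the secondary one.

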#### 7.2 Investigator Evaluations Quartile Improvement Score

Treating Investigators will compare:

- 1. Baseline photographs to one-month post treatment.
- 2. Baseline photographs to three-months post treatment.

A Quartile Improvement Scale will be used to individually score each category: (a) fine wrinkles, (b) skin texture, (c) dyschromia/pigment, (d) skin radiance, (e) pore size and (f) overall appearance.

Investigator Quartile Improvement Score				
Rating	Percentage (%)	Score		
No Improvement	0%	0		
Minor/Mild Improvement	1%-25%	1		
Moderate Improvement	26%-50%	2		
Marked Improvement	51%-75%	3		
Very Significant Improvement	76%-100%	4		

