### 4.2 Study Endpoints

### 4.2.1 Primary Endpoint

Primary Effectiveness Endpoint: improvement in the appearance of any one or more measurement of photoaging damage (fine wrinkles, skin texture, dyschromia/pigment, skin radiance, pore size and overall appearance) by the investigator using the quartile improvement score comparing standard 2D baseline

photograph and the 3 months post final treatment photograph. Reported percent change in improvement.

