### 4.2.2 Secondary Endpoint

Secondary Effectiveness Endpoint: improvement in the appearance of any one or more measurement of photoaging damage (fine wrinkles, skin texture, dyschromia/pigment, skin radiance, pore size and overall appearance) by the investigator using the quartile improvement score comparing standard 2D baseline photograph and the 1 month post final treatment photograph. Reported percent change in improvement.

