#### 4.2.4 Exploratory Endpoints

- i. Subject Modified Global Aesthetic Improvement Scale (GAIS) comparing their own photos at 3 months post treatments compared to baseline photos.
- ii. Subject Satisfaction with procedure recorded at 3 months post treatments.
- iii. Five (5) patients will have 2-mm punch biopsies from area of photoaging comparing baseline to 14 days and 3 months post treatments (location on face at discretion of investigating physician: either pre-auricular or at temple hairline. If face location is unattainable, the forearm, exposed to photoaging may be used as an alternate biopsy location). Pre- and post-treatment biopsies must be taken from the same general location for each patient.
- iv. Blinded Investigator: analysis of unmarked 2D photo sets via Canfield clinical system. Reviewers will select the order of baseline and post treatment onemonth photos. Then based on their selection assess photos for percentage improvement in photoaging damage using the quartile improvement scale and score 0-4. Reported percent change in improvement of correct order sets.
- v. Blinded Investigator: analysis of unmarked 2D photo sets via Canfield clinical system. Reviewers will select the order of baseline and post treatment three-months photos. Then based on their selection assess photos for percentage

improvement in photoaging damage using the quartile improvement scale and score 0-4. Reported percent change in improvement of correct order sets.

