10.2.3 Minimization of Bias and Potential Confounding Factors
Blinded investigator photo evaluation is intended to minimize bias.

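### Treating investigators who know the photograph order score the primary and secondary endpoints, while the masked reading of the same photographs is only exploratory and would need a scoring change before it could replace them

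*Combined protocol and SAP*

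**What the plan says.** - **Raters of the main endpoints.** Section 4.2.1 has the 3-month primary endpoint scored "by the investigator using the quartile improvement score comparing standard 2D baseline" and 3-month photographs. Section 4.2.2 has the 1-month secondary endpoint scored "by the investigator using the quartile improvement score comparing standard 2D baseline photograph and the 1 month post final treatment photograph". Section 7.2 identifies the raters: "Treating Investigators will compare" the baseline photographs with those at each follow-up. The visit descriptions in section 6.8 place the rating at Visits 6 and 7. No masking of these raters is described.
- **No comparator.** Section 4.1 states that there is no control group.
- **Bias control.** Section 10.2.3 consists of one statement: "Blinded investigator photo evaluation is intended to minimize bias".
- **Status of that reading.** Section 4.2.4 (iv and v) lists it as exploratory: "Blinded Investigator: analysis of unmarked 2D photo sets via Canfield clinical system". For the later time point, "Reviewers will select the order of baseline and post treatment three-months photos" and then rate improvement on the basis of that choice.
- **Content of that reading.** Section 7.7: "Two experienced, blinded photographic reviewers will compare 2D photographs via Canfield Scientific, Inc VISIA data access system". "A Quartile Improvement Scale will be used to individually score each category", with the same six categories and 0-4 scores as section 7.2. Sets placed in the wrong order are left out of the improvement score; the percentage correct is reported.
- **Test.** Section 10.2.2 and the SAP table compare the investigator's mean score with 0 by the Wilcoxon signed rank test, two-sided at 0.05, with no multiplicity correction. The blinded score has its own row with the same test.
- **Sample size.** Section 10.1 bases power above 95% at n = 25 on investigator-rated overall appearance at 3 months in an earlier study.

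**The concern.** A percent-improvement judgement made by someone who treated the subject and knows which photograph came later mixes treatment effect with expectation. With no control arm, nothing in the design subtracts the expectation. The plan recognises the problem and arranges a masked reading, but gives that reading no part in the primary or secondary conclusion and states no consequence if the two readings disagree. The safeguard therefore sits beside the result that it is meant to protect.

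The scale makes this worse. Its lowest score is no improvement, so a lenient rating cannot be offset by a harsh one. A null mean of 0 is true only if every subject scores exactly 0, which leaves the test no room for rating error.

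**Working it through.** **1. The plan's own figure.** Section 10.1 gives power above 95% at n = 25 but prints neither the mean nor the variance used, so the figure cannot be reproduced. Solving back for the standardised effect d = mean/SD at 95% power, two-sided alpha 0.05:
- normal approximation: d = (1.960 + 1.645)/√25 = 0.72
- adjusted for Wilcoxon efficiency: 0.721/√(3/π) = 0.74
- one-sample t (noncentral t): d = 0.75

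The claim is attainable if d is about 0.75 or more. Enrolment of 30 fits 25/(1 − 1/6) = 30, a dropout rate of 16.7% that the plan does not state. All of this concerns the investigator's rating, not the masked one.

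**2. How few lenient ratings are enough.** Zeros drop out of the signed-rank test and every non-zero score is positive. With k non-zero scores, the exact two-sided p = 2 × (1/2)^k:
- k = 5: p = 0.0625
- k = 6: p = 0.031

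So six subjects scored 1 and the rest 0 reach significance. That is 6/25 = 24%, or 6/30 = 20%.

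**3. Chance of significance with no true change.** Let q be the probability that an unchanged face is scored at least 1. The documents give no value; 10% to 40% is assumed. The chance is P(X ≥ 6) with X ~ Binomial(n, q):

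| q | n = 25 | n = 30 |
|---|---|---|
| 10% | 0.03 | 0.07 |
| 20% | 0.38 | 0.57 |
| 30% | 0.81 | 0.92 |
| 40% | 0.97 | 0.99 |

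The endpoint allows improvement in any of six categories. If a subject counts on any one of them, and a 5% lenient rate per category is assumed with independence, the rate per subject is 1 − 0.95^6 = 26%, and the chance of significance at n = 25 is 0.68.

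**4. Would the masked reading, as written, be safe as primary?** Suppose that reviewers guess the order at random and score half of the correctly ordered sets at least 1 (assumed). Wrong-order sets are dropped, so the chance that a subject contributes a positive score is 0.5 × 0.5 = 0.25, and no subject can contribute a negative one. P(X ≥ 6) with q = 0.25 is 0.62 at n = 25 and 0.80 at n = 30. Pure guessing would often be significant.

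**5. A scoring that works.** Section 7.7 has each reviewer rate on the basis of the chosen order, so a wrong-order set already carries a rating. Keep it and reverse its sign. If the reviewer is guessing, each rating is equally likely to be positive or negative, the scores are symmetric about 0, and the planned signed-rank test against 0 is valid. Averaging the two reviewers per subject preserves the symmetry, because exchanging the two photographs reverses both signs. This requires that display position gives no clue to the order.

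**The case against.** Much can be said for the plan. The blinded reading is prespecified at both time points, with a correct-order percentage and its own test, so a disagreement would be visible. Photography is standardised for views, lighting, make-up and a 15-minute indoor wait. The absence of a control group is explained by the before-after aim and the cleared device. The ranking of endpoints is openly stated and is not an internal error. The size of the exposure rests on an assumed q; at 10% it is only 0.03. All this stands, but standardised images do not control a rater's expectation, and a visible result with no stated role does not change the conclusion.

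Four stronger readings are tempting, and the documents do not support them.
- A reader might infer that one person gives all four treatments and then rates the subject. Section 7.2 uses the plural, and the visit descriptions in section 6.8 speak of the provider.
- A reader might infer that the plan formally declares success whatever the blinded result. No success rule is printed; the gap is that the blinded reading has no stated role.
- A reader might infer that promoting the blinded reading unchanged would remove the exposure. Step 4 shows that it would not.
- A reader might infer that masking would isolate the laser effect. Sections 6.2 and 6.4 have cleanser, moisturiser, sunscreen and, for some skin types, hydroquinone running alongside treatment with no control.

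**Conclusion.** The point holds and should be acted on. Both the primary and the secondary conclusion rest on treating investigators who know the photograph order, and the one stated bias control has no part in either. The word unblinded is not printed; it follows from the single-arm design and from photographs compared by time point. The figure that needs no leniency assumption is that six non-zero scores give p = 0.031. The range 0.03 to 0.97 at n = 25 depends on the assumed 10% to 40% leniency and on independent subjects. The masked reading is the better basis, but only once wrong-order sets are retained, and it addresses rater expectation alone.

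**What to change.** - Make the blinded 3-month reading (section 4.2.4 v) primary and the blinded 1-month reading (iv) secondary, with the treating investigators' scores as supportive. At minimum, conclude effectiveness only if the blinded 3-month test is also significant.
- In either case, replace the rule in sections 4.2.4 and 7.7 that drops wrong-order sets: analyse every set, and give a wrong-order set the negative of its rating.
- Average the two reviewers' scores per subject, since the plan states no rule for combining them. State that display order is random.
- Amend the synopsis and sections 4.2, 7.7, 10.1, 10.2.3 and the SAP table to match.
- In section 10.1, recalculate power for the masked score, or say that the figure above 95% applies only to the investigator's score. Print the earlier study's mean and SD.

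**Cost.** The reviewers, images and scale are already planned, so no new readers or photographs are needed. The masked result may be less favourable, and the present sample-size justification does not carry over.
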